### **7.2.2 Adverse Event Severity**

The severity of adverse events, including abnormal clinical laboratory values, will be assessed as 1-Mild, 2-Moderate, 3-Severe, 4-Life-threatening, and 5-Death. Refer to the study protocol Section 9.5 for criteria for defining the AE severity grades.

### **7.2.3 Adverse Event Relationship to HAV**

Causal relationship assessment of an AE to the HAV and index surgical procedure are as following:

- Not Related

- Unlikely Related
- Possibly Related
- Definitely Related

Refer to study protocol, Section 9.4 for the criteria for determining causal relationship.

#### **7.2.4 Serious Adverse Events**

An AE is considered “serious” if, in the view of either the investigator or Sponsor, it:

- Results in death.
- Is Life-threatening.
- Results in persistent or significant disability/incapacity.
- Results in congenital anomaly or birth defect.
- Requires inpatient hospitalization or leads to prolongation of hospitalization.
- Represents a medically important event as determined by the investigator.

#### **7.2.5 Adverse Event Summaries**

All AEs (serious and non-serious) occurring following the HAV implantation, regardless of relationship to the IMP, will be included and classified by SOC and PT using the current MedDRA.

For TEAEs, the following will be summarized and presented for the Safety analysis set:

- i. An overall summary of TEAEs, which includes:
    - a. the number and percentage of subjects experiencing a TEAE
    - b. the number and percentage of subjects experiencing a TEAE by strongest relationship to IMP
    - c. the number and percentage of subjects experiencing a TEAE by strongest relationship to study procedure(s)
    - d. the number and percentage of subjects experiencing a treatment emergent SAE (TESAE)
    - e. the number and percentage of subjects experiencing a TEAE leading to outcome of death
  - ii. the number and percentage of subjects experiencing a TEAE by SOC and PT
  - iii. the number and percentage of subjects experiencing a TEAE by SOC, PT and the strongest relationship to IMP
  - iv. the number and percentage of subjects experiencing a TEAE by SOC, PT and the strongest relationship to study procedure(s)
  - v. the number and percentage of subjects experiencing a TESAE by SOC and PT
  - vi. the number and percentage of subjects experiencing a related TESAE by SOC and PT
  - vii. the number and percentage of subjects experiencing a TEAE leading to outcome of death
-

by SOC and PT

A subject with more than one type of TEAE in a particular SOC will be counted only once in the total of subjects experiencing TEAEs in that particular SOC. Since a subject could have more than one type of TEAE within a particular SOC, the sum of subjects experiencing different TEAEs within the SOC could appear larger than the total number of subjects experiencing TEAEs in that SOC. Similarly, a subject who has experienced a TEAE in more than one SOC will be counted only once in the total number of subjects experiencing AEs in all SOCs.

All occurrences of all AEs and SAEs will be listed for each subject. The listing will contain the following information: verbatim term, SOC, PT, severity, relationship to IMP and study procedure(s), date and day of onset, date and day of resolution/death, action/intervention taken (Yes/No), the outcome, whether the event was an SAE or AESI, whether it led to study withdrawal and whether it is a TEAE. Listings will be sorted by subject identification number, onset date, SOC, and PT. If the onset date is completely missing, then these events will be presented first.

### **7.2.6 Events of Special Interest**

Adverse events constituting or leading to events of special interest related to interventions and infections will be presented descriptively. The analyses will include:

- HAV thrombosis: Number and percent of subjects experiencing the event, incidence rate of thrombosis (100 person-years of HAV exposure, censored at abandonment/renal transplant/early termination/death), and time from implantation to onset of the first event will be tabulated.
- HAV-related infection: Rate of HAV-related infections per100 person-years of HAV exposure (censored at abandonment/renal transplant/early termination/death), use of antibiotics, and the timing of first HAV-related infection relative to the initiation of dialysis using the HAV will be presented descriptively.
- Clinically significant (defined as severity of severe or greater, or requiring a surgical or radiological intervention) Stenosis of the HAV: Number and percent of subjects experiencing clinically significant stenosis, event rate (100 person-years of HAV exposure, censored at abandonment/renal transplant/early termination/death ), event by severity, and time from implantation to onset of the first event will be reported.
- Treatment Emergent AEs leading to revision of the HAV by SOC and PT
- HAV spontaneous rupture, anastomotic bleeding, and anastomotic rupture: Number and percent of subjects experiencing the event, event by severity, and the time from implantation to onset of the first event will be tabulated.
- HAV aneurysm: Number and percent of subjects experiencing the event of interest, incidence rate of aneurysms (100 person-years of HAV exposure, censored at abandonment/renal transplant/early termination/death), and time from implantation to onset of the first event will be presented.
- HAV pseudo-aneurysm: Number and percent of subjects experiencing the event of interest, event rate (100 person-years of HAV exposure, censored at abandonment/renal transplant/early termination/death), and time from implantation to onset of the first event will be presented. Only clinically significant (defined as requiring a surgical or

radiological intervention to repair the pseudo-aneurysmal segment) HAV pseudo-aneurysm is considered as an event of special interest and will be continually recorded in the eCRFs during the long-term follow-up period from 1 year to 3 years post-implantation.

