## 4.3 Duration of Study Participation

Each subject will be followed at study specific visits until he/she has completed 12 months of follow-up after implantation (irrespective of patency status). After 12 months, subjects with a patent HAV will be followed (while the HAV remains patent) for up to 3 years (36 months) post-implantation at study visits every 6 months.

The expected duration of the clinical investigation is 40 months (initiation of enrollment through completion of data collection).

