### 2.2 Endpoints

#### 2.2.1 Primary Endpoints

##### 2.2.1.1 Primary Safety Endpoints – assessed at 3 months post implantation

- Adverse events indicating possible mechanical failure or weakness of the HAV
  - Anastomotic rupture
  - Anastomotic bleeding
  - Spontaneous HAV rupture
  - Aneurysm
  - Pseudoaneurysm
  - Abnormal post cannulation hemostasis
- HAV infections
- Change from baseline of panel reactive antibody (PRA) and anti-HAV IgG levels (at 2

months)

- All adverse events (AEs)/serious adverse events (SAEs) and adverse events of special interest

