## 4.4 Handling of Dropouts or Missing Data

### 4.4.1 Time-to-Event Analyses

The following censoring rules will apply to all “time to event” analyses:

- Subjects who have patent HAV at the time of death, kidney transplant or withdrawal will be censored at that timepoint.
- Subjects who are lost to follow-up with a patent HAV will be censored at their last known visit.
- Subjects lost to follow up whose HAV was not patent at the last completed visit will be treated as abandoned at the time of HAV occlusion and recorded in the eCRFs.
- Subjects in whom a delayed decision is made to abandon the HAV (e.g. delayed and then failed thrombectomy) will have the date of abandonment recorded as the date of the initial recognition of the thrombosis, not the date that a final decision is made.

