### **7.1 Extent of Exposure**

There are two exposures that will be summarized:

1. Subject exposure during the study period is defined as the length of time from implant to explant, death or early termination (e.g. lost to follow up, withdrew consent etc.).

2. Subject exposure to a patent HAV used for hemodialysis is defined as the length of time from first cannulation to explant, abandonment, death, transplant, or early termination (e.g. lost to follow up, withdrew consent etc.).

Subject exposure during the study period and exposure to a patent HAV used for hemodialysis will be reported at each analysis time point. Descriptive statistics will be provided for days of exposure. Overall exposure will be summarized in total subject-years. This will be calculated as follows:

Exposure in subject-years = Sum of duration of exposure in days (for all enrolled subjects) / 365.25.

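### HAV-related infection, a primary safety endpoint, is summarised only by a rate that stops at abandonment, so observed infections of an abandoned but retained HAV fall outside its only named frequency measure

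*SAP*

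**What the plan says.** HAV infections are listed in SAP 2.2.1.1 under "Primary Safety Endpoints – assessed at 3 months post implantation", and again in SAP 2.2.2.1 as a secondary safety endpoint through 36 months.

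SAP 7.2.6 gives one frequency measure for them: "Rate of HAV-related infections per100 person-years of HAV exposure (censored at abandonment/renal transplant/early termination/death"). It adds antibiotic use and the timing of the first infection relative to dialysis through the HAV, but no count of subjects. The other named HAV complications in that section do have one, for example "HAV aneurysm: Number and percent of subjects experiencing the event of interest, incidence rate of aneurysms".

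Four other places bear on this:

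- **Meaning of abandonment.** SAP 2.2.1.2 defines it by the absence of any HAV segment from the dialysis circuit. Explantation is not required, and SAP 3.2.4 says the HAV stays in place unless the investigator judges that it must come out.
- **Follow-up.** Protocol 4.3 follows every subject to 12 months "irrespective of patency status". SAP 7.2 has all adverse events reported to Month 12 or early termination. After Month 12 only subjects with a patent HAV are followed.
- **Exposure.** SAP 7.1 already defines a subject exposure as "the length of time from implant to explant, death or early termination". Abandonment does not end it.
- **Dating.** Under SAP 4.4.1, subjects with a delayed decision to abandon "will have the date of abandonment recorded as the date of the initial recognition of the thrombosis". That list opens with "The following censoring rules will apply to all “time to event” analyses".

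**The concern.** Stopping the clock at abandonment suits thrombosis or stenosis, which concern a conduit in use. Infection concerns material that is still in the arm. A subject whose HAV is abandoned at Month 4, left in place and infected at Month 7 is still attending visits and reporting adverse events, yet that infection falls outside the one rate named for the endpoint.

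The gap would be minor if SAP 7.2.6 also gave an uncensored number and percent of subjects, but for infection it does not. A reader looking for the result on HAV infections will go to this rate, in a study meant to confirm the short-term safety of the product from the new manufacturing system.

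**Working it through.** The documents state no infection rate or person-years, so there is no plan figure to reproduce. The calculation below only sizes the effect.

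**Inputs**
- N = 30 implanted, the planned maximum (SAP 3.1).
- Secondary patency S from the pooled earlier dialysis studies: 97% at 6 months and 91% at 12 months (Protocol 2.3.2.1).
- Assumptions: straight lines between these points, starting at 100%, so S(3 months) = 98.5%. Deaths, transplants and dropouts are ignored.

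**Person-years to abandonment** = N × area under S
- To 3 months: 30 × 0.25 × (1 + 0.985)/2 = 7.44, against 30 × 0.25 = 7.50. Lost: 0.06 (0.75%).
- To 12 months: 30 × [0.5 × (1 + 0.97)/2 + 0.5 × (0.97 + 0.91)/2] = 30 × 0.9625 = 28.9, against 30.0. Lost: 1.1 (3.75%).
- A constant hazard fitted to 91% alone gives 30 × 0.09/0.0943 = 28.6, so 1.4 lost. The result is not sensitive to the shape of the curve.

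**Expected abandonments** = N × (1 − S); **chance of at least one** = 1 − S^30
- 3 months: 30 × 0.015 = 0.45; 1 − 0.985^30 = 36%. The documents give no 3-month figure. If 3-month abandonment were 10%, these become 3.0 and 96%.
- 12 months: 30 × 0.09 = 2.7; 1 − 0.91^30 = 94%.

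**12-month rate per 100 person-years, for assumed event counts**

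| Infections before / after abandonment | Planned rate | Not stopped at abandonment |
|---|---|---|
| 0 / 1 | 0/28.9 = 0 | 1/30 = 3.3 |
| 1 / 0 | 1/28.9 = 3.5 | 1/30 = 3.3 |
| 1 / 1 | 1/28.9 = 3.5 | 2/30 = 6.7 |

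Exact Poisson 95% limits for the first row are 0 to 12.8 (planned) and 0.1 to 18.6 (not stopped). At 3 months a single infection counted over all followed time gives 1/7.5 = 13.3 (0.3 to 74.3).

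**How many infections to expect.** Protocol 2.3.2.1 reports 3 access-site infections in more than 150 years of follow-up, at most 2 per 100 person-years. Over 30 person-years that is about 30 × 0.02 = 0.6. If the same rate held after abandonment (an assumption), the expected number excluded is 1.1 × 0.02 = 0.02, or 1.4 × 0.02 = 0.03 with the constant hazard.

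The table takes the planned rate to drop both events and person-time after abandonment. The SAP does not say so. If only person-time stopped, numerator and denominator would not match.

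**The case against.** The strongest case on the other side has five parts.

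1. **Nothing disappears from the report.** SAP 7.2.5 tabulates all treatment-emergent events by system organ class and preferred term, with number and percent and no cut at abandonment, and lists every event with a special-interest flag. This stands. A reader might infer that these infections go unreported; the documents do not support that. What is missing is a planned line that totals subjects with HAV-related infection, since such events may be spread over several preferred terms.

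2. **Downward bias is not shown.** It is tempting to infer that the rule makes the rate look better. That requires a higher infection rate after abandonment than before, and neither document says so. The second row of the table goes the other way, 3.5 as planned against 3.3. The contrast of 3.5 with 6.7 in the third row follows only from placing one infection in about 1.1 person-years. This stands.

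3. **The effect is small where the endpoint is primary.** The primary assessment is at 3 months, when 0.06 of 7.5 person-years is lost and there is a 64% chance of no abandonment at all. This stands; the point carries more weight at 12 months, where infection is a secondary endpoint.

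4. **Back-dating may not apply.** The rule in SAP 4.4.1 is written for time-to-event analyses, and a rate per 100 person-years is not named there. A reader might take it as settled that infections around a later failed thrombectomy are excluded too. That follows only if the same recorded date is used for this rate, which the SAP does not say. Censoring at abandonment carries the point without it.

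5. **One denominator for all events is a fair choice.** Thrombosis, stenosis, aneurysm and pseudoaneurysm use the same one, and the study is descriptive. This is a reason to keep the planned rate, not a reason to have no other measure for infection.

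**Conclusion.** The concern holds in a limited form. The only frequency measure that the SAP names for HAV-related infection stops at abandonment, while the HAV can stay in the arm and adverse events are still collected to Month 12. Observed infections can therefore be left out of it, and no count of subjects makes up for that.

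The lost person-time is small: 0.75% at 3 months and 3.75% at 12 months under the patency assumptions above. An excluded infection is also unlikely if the earlier access-site infection rate carries over. But with fewer than one infection expected in 30 person-years, a single excluded event would decide whether the 12-month rate reads zero or about 3.3 per 100 person-years. The two intervals overlap widely, so this affects how a descriptive result reads; no test is involved. The direction of any effect is unknown.

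**What to change.** In SAP 7.2.6, for HAV-related infection:

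- Add the number and percent of subjects, and a rate per 100 person-years, counted from implantation to explant, death or early termination/end of follow-up (the first exposure in SAP 7.1) and not stopped at abandonment.
- State how renal transplant is handled, because that exposure does not list transplant as an end point while the planned rate does.
- Note that after Month 12 follow-up ends when patency is lost, so the added rate covers time after abandonment only up to Month 12.
- Keep the planned rate as a second line. Say whether events after abandonment leave its numerator, and whether the back-dated abandonment date of SAP 4.4.1 applies to it.

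The cost is one extra table line from data already collected, and a reported rate that may move slightly either way. This is a cheap improvement.

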### **7.3 Clinical Laboratory Assessments**

Blood samples will be collected for clinical chemistry and hematology testing at the following study visits: Screening, Day 28, and Months 2. In addition, laboratory testing at the Screening visit will include INR or Prothrombin time and a serum or urine pregnancy dipstick test for women of childbearing potential in order to help ensure the eligibility and safety of prospective subjects. Hematology and clinical chemistry, pregnancy test (serum or urine) and INR/ Prothrombin time samples will be analyzed at the study site's local laboratory. Blood samples will be collected for PRA/anti-HAV IgG analysis at the visits presented in Appendix A; these samples will be analyzed at a central laboratory.

Continuous clinical laboratory values will be summarized by presenting descriptive statistics of raw data and change from baseline values at each time point.

Laboratory parameter results from unscheduled visits will be excluded from table summaries but will be included in data listings.

Listings will include flags for values outside of the reference ranges, and clinical significance if a laboratory result is deemed abnormal.

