Microscopic analysis indicated that the HAV integrated with the host tissue. The cellular host response to the HAV demonstrated smooth muscle actin-positive cells within the vessel wall, endothelial cells lining the lumen, and an adventitial-like outer layer adjacent to the HAV similar to that of native blood vessels. Calcification was not observed. The HAV were therefore populated with cell types characteristic of healthy native vasculature. Immunostaining showed that collagen type I, collagen type III, and fibronectin within the vessel wall displayed a more organized structure with more circumferential alignment after 6 months. Additionally, collagen type I, glycosaminoglycans, and elastin deposition increased over this time period. The observed changes in organization and composition of ECM components indicated that, aided by infiltration of host vascular cells, HAV were re-modeled *in vivo* in a manner that mimicked the dynamic re-modeling process of native blood vessels.

The HAV did not elicit biologically-significant humoral or cellular immune response. Analysis of panel reactive antibody (PRA) levels showed no increase for any animal, indicative that the HAV did not cause production of the anti-human antibodies measured by this assay. In an *in vitro*

T-cell proliferation assay, low stimulation rates (3% to 17%; at or below that of negative control) were observed when buffy coat cells from each animal were cultured with HAV material. Increases in immunoglobulin G (IgG) titer to the ECM, defined as > 25 fold titer increase over baseline, were observed in all study animals regardless of HAV functional outcome. In addition to the implant of the HAV test article, an additional test article consisting of a micronized extract of the HAV, as well as phosphate-buffered saline (negative control), were injected intra-dermally into the upper hip/thigh of all animals to monitor for the development of a delayed-type hypersensitivity immune response. No delayed-type hypersensitivity reactions were observed in any animals.

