### **2.3.3.1 CLN-PRO-V002 Study Results (24 M)**

Recruitment began in October 2013 and was completed in June 2014 with 20 patients implanted. Thirteen patients completed the 2 year follow up visit. Of the 7 patients terminating the study early, 3 died and 4 were withdrawn after occlusion of the HAV. None of the deaths were considered related to the investigational device or procedure.

Kaplan-Meier analyses in which deaths were censored revealed primary, primary assisted, and secondary patency probability rates of 79.2%, 79.0%, and 89.5% at Week 26, 63.3%, 63.2%, and 84.2% at Month 12, 63.3%, 63.2%, and 79.0% at Month 18, and 58.1%, 57.9%, and 73.7% at Month 24.

Six patients (30%) required at least 1 graft intervention to maintain or restore HAV patency during the study. Four patients required 1 intervention and 1 patient each required 3 and 4 interventions. Most interventions successfully restored patency. However, in 1 patient the graft patency could not be restored and the HAV was replaced with an alternative bypass graft. Two patients, who had previously undergone successful interventions, developed a recurrent thrombosis which was not treated and the HAV was left occluded. Two patients experienced HAV thrombosis with no or minimal symptoms and refused interventions on the HAV.

All 20 patients experienced AEs (a total of 92 events). Thirty-one of these events in 13 patients were considered serious. The most frequent AEs reported included graft thrombosis (35% of patients), anastomotic stenosis (20% of patients), lymphocele (20% of patients), and local swelling (15% of patient). Those serious adverse events (SAEs) reported by at least 2 patients were graft thrombosis (6 patients, 30%) and anastomotic stenosis (2 patients, 10%).

No patient showed an increase in PRA levels. Two patients had a significant (> 2 fold) increase from baseline in IgG levels. One of these patients experienced a thrombosis of the HAV between 3 and 6 months after implantation, while the other patient has had no HAV-related AEs and continues to have primary patency. Neither patient has had any evidence of dilatation or structural degeneration of the HAV.

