### 4.2 Study Endpoints

#### 4.2.1 Safety Endpoints

##### 4.2.1.1 Primary Safety Endpoints – assessed at 3 months post implantation

- Adverse events indicating possible mechanical failure or weakness of the HAV
  - Anastomotic rupture
  - Anastomotic bleeding
  - Spontaneous HAV rupture
  - Aneurysm
  - Pseudoaneurysm
  - Abnormal post cannulation hemostasis
- HAV infections
- Change from baseline of PRA and anti-HAV IgG levels (at 2 months)
- All AEs/SAEs and adverse events of special interest.

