#### **4. GENERAL CONSIDERATIONS FOR DATA ANALYSIS**

CTI Clinical Trial and Consulting Services will perform all efficacy and safety statistical analyses described in this SAP. Any change to the data analysis methods described in the protocol will require an amendment of this SAP only if it changes a principal feature of the protocol. Any other change to the data analysis methods that are described in the protocol, and the justification for making the change, will be described in the clinical study report. Additional exploratory analyses of the data will be conducted as deemed appropriate.

The analyses for this study will be performed as follows:

- The primary analysis will be performed after the last subject completes 3 months of follow-up.
- A second analysis will be performed after all subjects have completed 12 months of follow-up.
- A final analysis will be performed after the last subject completes 36 months of follow-up.
- Interim safety data will be provided periodically to the Data Monitoring Committed (DMC) as per the DMC Charter.

A soft database lock will be required for the data included in the planned primary (3 months) and second (12 months) analyses. A final hard lock will be required for the final analysis at 36 months.

Statistical analyses will be primarily descriptive in nature. Unless otherwise specified, continuous variables will be summarized by presenting the number of non-missing observations, mean, standard deviation, median, inter-quartile range, minimum and maximum. Categorical variables will be summarized by presenting the number of subjects and percentage for each category.

All tabulations will be based on pooled data across centers.

Analyses will be performed using SAS for Windows statistical software, version 9.4 or higher (SAS, Cary, NC), except where other software may be deemed more appropriate.

Subject data will be listed and sorted by subject number.

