### **4.5 Data Derivations and Transformations**

Not applicable.

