## **7. SAFETY ANALYSIS**

Safety data include results from laboratory testing (clinical chemistry, hematology, anti-HAV IgG antibodies, and PRA), adverse events, findings from symptom directed physical exams and Duplex ultrasound results. All safety summaries (or analyses if applicable) will be conducted using the Safety analysis set.

Screening laboratory testing will include International Normalized Ratio (INR) or Prothrombin time, and a serum or urine pregnancy dipstick test for women of childbearing potential in order to help ensure the eligibility and safety of prospective subjects.

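### Anti-HAV IgG, a primary safety endpoint at 2 months, is summarised only as raw values and arithmetic change, with no fold-change, log-scale or responder summary

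*SAP*

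**What the plan says.** Protocol 4.2.1.1 lists "Change from baseline of PRA and anti-HAV IgG levels (at 2 months") among the primary safety endpoints, and SAP 2.2.1.1 repeats it. Neither states the scale of the change. Protocol section 9 also names an increase from baseline in these antibodies as a safety measure, without saying what counts as an increase.

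SAP 7 treats IgG as laboratory data: "Safety data include results from laboratory testing (clinical chemistry, hematology, anti-HAV IgG antibodies, and PRA"). The laboratory rule in SAP 7.3 therefore applies, and it gives "descriptive statistics of raw data and change from baseline values at each time point". The default statistics in SAP 4 are the "number of non-missing observations, mean, standard deviation, median, inter-quartile range, minimum and maximum"; a geometric mean is not among them. The entry under "4.5 Data Derivations and Transformations" reads "Not applicable".

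The Protocol reports earlier IgG results as follows:

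- **Baboon studies (2.2):** titer increases, "defined as > 25 fold titer increase over baseline", in all animals.
- **Pooled dialysis studies CLN-PRO-V001 and V003 (2.3.2.1):** titers rose in 5 of 60 subjects; no criterion is stated.
- **Peripheral arterial study CLN-PRO-V002 (2.3.3.1):** "Two patients had a significant (> 2 fold) increase from baseline in IgG levels", out of 20 implanted.

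**The concern.** An antibody titer is a multiplicative quantity, and a rise is naturally read as a ratio to the subject's own baseline. An arithmetic difference mixes that ratio with the starting level, so the same biological response produces very different entries in the planned table. If baselines vary widely, one or two high-baseline subjects can set the mean and standard deviation of change.

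What is at stake is the immunogenicity part of the primary objective. The study asks whether Luna behaves like the product used before, and the earlier human IgG results are counts of subjects with an increase. A mean arithmetic change cannot be set beside such a count. The study is open-label and the SAP fixes no fold threshold, so any threshold would be chosen after the data have been seen.

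**Working it through.** The plan gives no IgG figure, variance or sample size calculation, so there is no figure of its own to reproduce. The check has three parts. Titer values and variances below are assumptions; only the counts and n = 30 (the planned maximum) come from the documents.

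**1. Scale.** With baseline b and fold rise f, arithmetic change = b x f - b = b x (f - 1).

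| Baseline | 1.25-fold | 2-fold | 4-fold |
|---|---|---|---|
| 50 | 12.5 | 50 | 150 |
| 400 | 100 | 400 | 1200 |
| 6400 | 1600 | 6400 | 19200 |

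A 1.25-fold drift at 6400 (+1600) exceeds a 4-fold rise at 50 (+150). Effect on the mean of 30 otherwise unchanged subjects:

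- Two 4-fold responders at baseline 50: 2 x 150 / 30 = 10.
- One 1.25-fold drift at baseline 6400: 1600 / 30 = 53.

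**2. Comparison with earlier results.** CLN-PRO-V002 gives 2/20 = 10% above 2-fold. The planned table has no entry that corresponds. A count of subjects above 2-fold would. The dialysis studies give 5/60 = 8.3%, but without their criterion no summary of this trial can be matched to that figure.

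**3. Does the scale change what is seen?** Simulation with n = 30, three subjects with a true 4-fold rise, lognormal baselines, within-subject log2 SD of change 0.5 and 20,000 trials. The table shows the share of trials in which the statistic exceeds its own 97.5th percentile under no response.

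| Assumed log2 SD of baseline | Mean arithmetic change | Geometric mean ratio |
|---|---|---|
| 0.5 | 91% | 60% |
| 1 | 73% | 60% |
| 1.5 | 46% | 60% |
| 2 | 27% | 60% |

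The group-mean comparison reverses between SD 1 and SD 1.5. With the SD of change raised to 0.71, the geometric mean ratio still leads at baseline SD 1.5, but by less (29% versus 35%). The planned median barely responds: it exceeds its limit in 9% to 11% of trials.

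Finding individual responders does not reverse. The largest ratio belonged to a true responder more often than the largest arithmetic change in every case tried (baseline SD 0.5 to 2, SD of change 0.5 and 0.71): 97% to 99.9% against 65% to 99%. At SD of change 0.5 the arithmetic figure is 99% at baseline SD 0.5, 95% at SD 1 and 76% at SD 2, each against about 99.9% for the ratio.

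**The case against.** Several arguments on the other side have force.

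- **Assay unit.** This trial's documents speak of IgG levels or values. The word titer appears only for earlier studies, and the central assay's unit is not given. This stands: the weighting argument is conditional on a ratio-type readout. It is also a reason to state the scale.
- **Data remain available.** SAP 4 plans subject listings and allows further exploratory analyses, so up to 30 ratios could be worked out by hand, and the planned maximum would expose an extreme riser. This makes it a reporting gap and not a loss of data. It does not replace a summary and threshold fixed in advance.
- **A geometric mean ratio alone would not help.** One 64-fold riser among 30 otherwise unchanged subjects gives 64^(1/30) = 1.15, while the planned maximum change, from 100 to 6400, shows 6300 plainly. Nor can a geometric mean ratio be set beside 2 of 20. This stands, and it is why the fix puts the count first.

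A reader might also infer three stronger claims that the documents do not support:

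- **That the table orders subjects by baseline.** It is a group summary and ranks no one. Change depends on baseline and fold together. In simulation with median fold 1.5 to 2 and SD of ln fold 0.2 to 0.7, its rank correlation with baseline ran from 0.16 to 0.94, reaching 1.00 only when all subjects share one fold rise.
- **That the whole program measures IgG response as fold change.** A fold criterion is stated for CLN-PRO-V002 and the baboons, with different thresholds. The dialysis studies, which share this trial's indication, state none.
- **That arithmetic change is generally insensitive.** For the group mean, that depends on an assumed baseline spread and reverses when the spread is small. The study also tests no hypothesis, so detection is only a rough yardstick.

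**Conclusion.** The point holds in this form: the SAP gives no fold-change, log-scale or responder summary for a primary immunogenicity endpoint. The 2-month table therefore cannot be set beside the more than 2-fold count in CLN-PRO-V002. If the assay reports titers, its mean change is weighted toward subjects with high baseline values.

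The absence of a ratio or responder summary follows directly from SAP 4, 4.5 and 7.3. The size of the weighting does not, because the documents give no IgG distribution. Any gain in group-mean sensitivity needs a wide baseline spread (assumed log2 SD of about 1.5 or more) and reverses at SD 1 or less. Better identification of individual responders on the ratio scale held across the whole assumed range. The data collected are adequate; only the planned summary needs to change.

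**What to change.** In SAP 4.5 and 7.3, for anti-HAV IgG:

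- State the assay's reporting scale.
- Derive each subject's ratio to baseline, with a stated convention for values below the assay limit so that subjects negative at baseline keep a ratio.
- At each visit report the number and percent of subjects above a fold rise fixed before the 3-month lock, including more than 2-fold for comparison with CLN-PRO-V002.
- At each visit also report the individual ratios with median and range, and the geometric mean ratio with 95% CI.
- Keep PRA on its own scale.

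If the criterion behind the 5 of 60 in the dialysis studies can be recovered, add a count on that criterion too.

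The cost is SAP wording, one derived variable and the below-limit convention, which is somewhat arbitrary and affects ratios for subjects near the limit. No new samples, visits or assays are needed.
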